To date, the impact of nutrient warning labels has not been tested in a real-world randomised controlled trial (i.e., in a restaurant), or in a UK context. Recent work suggests that UK consumers support the introduction of nutrient warning labels, and their PME was rated as significantly higher relative to a control label (QR code) (13). This study aims to test the effect of a menu featuring salt warning labels (design informed by previous work (13)) on perceived message effectiveness relative to a menu with no labels in a real-world restaurant environment. The study will also act as a pilot experiment for examining the impact of the salt warning label on food choice and subsequent salt intake in real-world conditions.

Primary objectives:

- To measure the PME of a menu featuring salt warning labels relative to a menu with no labels
- To measure label awareness, perceived knowledge gain, and perceived influence of the label on food choice

Secondary objectives:

- To identify whether there is an effect of the salt warning label on:
 - Food choice (label/no label)
 - Total salt selected
 - Total salt intake
- To examine support for the introduction of a salt warning label policy in the UK

Experimental design

The study will be a between-subjects randomised controlled trial design. The between-subject factor is the menu labelling. In the experimental condition, a nutrient warning label will be placed next to menu items that are high in salt. In the control condition, there will be no labels. The outcome will be (i) perceived message effectiveness, (ii) salt selected, label (y/n) selected, and salt intake. This will allow us to examine whether the salt warning label intervention impacts perceived message effectiveness and food choice relative to the control condition.

Participants and recruitment

Recruitment

Participants will be recruited via social media adverts (Facebook, Instagram), a database maintained by researchers at the University of Liverpool, and word of mouth. Interested participants will be asked to click a link which will take them to an online screening questionnaire (Appendix A). Participants can bring a maximum of nine guests to the restaurant. Guests will be pre-screened in advance to ensure eligibility. In pre-study instructions participants will be informed that any guests they bring will participate in the study.

Sampling

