We will stratify based on education level to be largely representative of the UK population (14, 15). We will recruit (approximately):

- 50% NQF 4 Level 4 or above (University degree or equivalent) and 50% NQF Level 3 or below (no University degree)

We will also aim to fulfil the following quotas for age and gender, based on the composition of the UK population (16, 17):

- 50% 18 – 39 and 50% 40 and over
- 50% female and 50% male

We will only recruit up to 10% of the sample as current University students. Students have a high SEP in terms of education, but typically have low disposable income, which may impact relative health motives. This could distort the results if students are recruited in high numbers.

Inclusion and exclusion criteria

Participants are eligible to take part if they:

- Are a UK resident
- Are aged 18 years and above
- Are fluent in English
- Eat an out-of-home meal at least once a month on average
- Have no dietary allergies
- Are not vegan

There are no additional exclusion criteria as this is a real-world study.

Methods

Procedure

Participants will be asked to attend one session at a restaurant from Monday – Saturday between 12 – 5pm. All participants will be asked to verbally consent to taking part in the study, and will be given the opportunity to ask questions before the study begins.

Participants will be asked to order lunch from a menu. The menu will either feature nutrient warning labels next to the relevant menu items (experimental condition), or no labels (control condition). A researcher will ask participants to write their order down on an order form, communicate the order with the kitchen, photograph the meal when it is ready to be served, and photograph the plate when the participant is finished with the meal in order to estimate amount consumed.

After finishing their meal, participants will be asked to fill out an online questionnaire (on an iPad) about their sociodemographic characteristics, health motives, label awareness, salt awareness, perceived message effectiveness, perceived knowledge gain, perceived influence, and support for the introduction of a restaurant salt warning label policy in the UK. The questionnaire will also ask (i) whether any food or drink items were shared with other participants, and, if so, what item(s) were shared and (ii) whether they added any condiments to their meal (see Appendix E).

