PME will be measured using an adapted version of the UNC PME scale. The scale measures health concern, product attitude, and discouragement of product consumption (21). Participants will answer 3 PME questions using a Likert scale ranging from 1 – 5 anchored by “not at all” and “a great deal”: Prompt: “Think back to the menu that you ordered from...” “The menu made me concerned about the health effects of consuming items high in salt”, “The menu made consuming items high in salt seem unpleasant”, “The menu discouraged me from wanting to consume items high in salt”. The mean response to the three items will be calculated. PME is used as an early indicator of a health message’s potential to change behaviour (e.g., reduce selection of items high in salt) (22). The scale has been used extensively in similar experiments to identify the potential impact of nutrient warning labels, has strong construct validity, and is predictive of longer-term actual behaviour (21, 23-28).

An attention check will be placed after the PME questions. “This question is an attention check, so please answer truthfully. How many times have you visited the planet Mars? Several times / Just once / Never”.

Correct answer: Never

Label awareness

"Did you notice any warning labels next to any of the menu items when making your meal selection?" (yes/no).

If [yes], "What did the label tell you about?" Response options: Healthy items, Organic, Calcium, Sustainable, Added sugars, Vegetarian, Unhealthy items, Salt, Fibre, Gluten Free, None of these, Not sure.

If [yes], "Please describe what the label said" (open text response). Responses that mention high in salt or similar will be coded as aware.

Salt awareness

"Did you think about the salt content of the meals when making your selection?" (yes/no)

Note: For the below questions, both groups will be shown an image of the labelled menu. Some question phrasing is slightly altered for the control condition.

Perceived knowledge gain

"Did you learn something new from the salt labels on the menu?" (yes/no).

Control: Same as above

Perceived influence

"Did the salt label influence which food you ordered from the menu" (yes/no).

"If [yes], how did the salt label influence your choice?" Response options: I avoided choosing a meal high in salt; I chose a meal high in salt; Other (free text response)

Control: "Would the salt label have influenced what food you ordered from the menu?" (yes/no)

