
 - Participants will receive a standard menu without nutrient warning labels. 	
 - Participants will receive a menu featuring a nutrient warning label next to items high in salt. Text at the bottom of the menu will read “[label image] indicates that the salt content of this item is higher than 50% of the daily recommended limit (6g per day). High salt 				

		intake can increase blood pressure and risk of heart disease and stroke.”
	
 - The participants will be asked to order lunch from the menu and a drink (optional) and write this down on an order form (Appendix D) - A researcher will communicate the order with the kitchen, take a photo of the meal when it is ready to be served and take a second photo when the participant is finished with the meal. The researcher will send themselves each photo on WhatsApp labelled with the participant ID. 	
Post-meal assessments (Qualtrics) (Appendix E)	
 - After finishing their meal, participants will be provided with an iPad. They will answer a question about what they think the aim of the study was in an open-ended response format. - Next, participants will complete measures of PME, label awareness, salt awareness, perceived knowledge gain, perceived influence, and policy support. - Finally, participants will answer questions on demographic characteristics (including frequency of eating OOH) and health motives. 	
Later intake	
 - After the restaurant visit (same day), participants will receive a link to an online questionnaire assessing their dietary intake for the rest of the day after the restaurant visit, to be completed before they go to bed (Intake24). - This will enable us to calculate salt consumed post intervention for the rest of that day. - They will also be requested to answer some additional questions on demographic characteristics. 	
Additional demographic questions (Appendix F) and debriefing (Appendix G) (Qualtrics)	
 - After completing the dietary intake questionnaire, participants will be asked to answer some additional questions on demographic characteristics. - Upon completion, participants will be debriefed on study aims. 	

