Reimbursement	
 - Participants will receive £25 which will likely cover their lunch costs and serve as an incentive for people from different SEP strata to participate. Participants will either (i) pay for their own meal at the restaurant and receive £25 via invoice or (ii) have their meal paid for by a researcher using a prepaid card; if this costs less than £25, they can request to receive the remaining amount via invoice, if this costs more than £25, they will need to pay the difference at the restaurant. 	

Statistical analysis

Participant characteristics

Participant characteristics will be presented overall and by experimental condition in a table. Data will include age, gender, ethnicity, highest educational qualification, employment status, BMI, frequency of eating OOH, and hunger. Continuous variables will be summarised as means and standard deviations, and categorical variables will be summarised as counts and percentages.

Measured variables

Primary

A linear regression will be used to assess differences between menu conditions in terms of PME. The between-subjects predictor will be label condition, and the dependent variable will be PME.

Highest education level (categorical: NQF level 4 or above, NQF level 3 or below) will be included as a covariate in the model to account for stratification (30). Health motives (continuous) will be included as a covariate as this may predict outcomes (e.g., health motivated individuals may be more likely to believe a menu with labels will change their behaviour) (30). Age and gender will also be included as covariates as previous work suggests that this can influence ratings of label PME and salt intake (13).

Descriptive analysis will be used to report (overall and by condition) participants' label awareness, salt awareness, perceived knowledge gain, perceived influence, and policy support (dichotomised into support/oppose). Logistic regressions will be performed to assess the odds of (i) being aware of the label, and (ii) being aware of the salt content of the meals in the labelled menu group, using the control menu group as the reference category. The same covariates as above will be included.

Secondary

Linear regressions will be performed to assess differences in menu conditions in terms of total salt purchase and total salt intake. The same covariates as above will be included.

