Start of Block: Additional assessments

Display This Question:

If Please select the letter which is circled on your sticker label. If you are unsure, please ask th... = B

Here is the menu you ordered from. The menu features salt warning labels next to items that exceed 50% of the daily recommended limit for salt intake: [menu B image]

Display This Question:

If Please select the letter which is circled on your sticker label. If you are unsure, please ask th... = A

Here is a slightly different version of the menu you ordered from. The menu features salt warning labels next to items that exceed 50% of the daily recommended limit for salt intake: [menu B image]

Did you learn something new from the salt labels on the menu?

Yes (1)

No (2)

Display This Question:

If Please select the letter which is circled on your sticker label. If you are unsure, please ask th... = B

Did the salt labels influence which food you ordered from the menu?

Yes (1)

No (2)

Display This Question:

If Did the salt labels influence which food you ordered from the menu? = Yes

How did the salt label influence your choice?

I avoided choosing a meal high in salt (1)

I chose a meal high in salt (2)

Other (please describe) (3) _____

Display This Question:

If Please select the letter which is circled on your sticker label. If you are unsure, please ask th... = A

Would the salt labels have influenced which food you ordered from the menu?

Yes (1)

No (2)

Display This Question:

If Would the salt labels have influenced which food you ordered from the menu? = Yes

How would the salt labels have influenced your choice?

- I would have avoided choosing a meal high in salt (1)
- I would have chosen a meal high in salt (2)
- Other (please describe) (3) _____

If the UK Government introduced policy requiring restaurant menu items high in salt to feature these labels, how would you feel?

- Strongly oppose (1)
- Oppose (3)
- Neutral (4)
- Support (5)
- Strongly support (6)

Please use this box to add any additional thoughts which you may have about the salt label.

End of Block: Additional assessments

Start of Block: Demographics

What is your age (in years)?

What is your sex? A question about gender identity will follow.

- Male (1)
- Female (2)

Which of the following best describes your gender?

- Man (1)
- Non-binary (2)
- Woman (3)
- Prefer to self-describe (4) _____
- Prefer not to say (5)

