What is your highest educational qualification? If you are a student, please select the qualification being studied for.

- Less than high school (no formal qualifications) (1)
- High school completion (e.g., GCSEs or equivalent) (2)
- College or foundation degree (e.g., A Levels or equivalent) (3)
- Bachelor's degree (4)

- Master's degree (5)
- Doctorate or professional degree (6)

What is your current employment status?

- Full-time (1)
- Part-time (2)
- Student (3)
- Retired (4)
- Unable to work due to sickness/disability (5)
- Looking after home/family (6)
- Unemployed (7)
- Other (please describe) (8) _____

What is your ethnic group? Choose one option that best describes your ethnic group or background.

- Asian or Asian British** Bangladeshi Chinese Indian Pakistani Any other Asian background (3)
- Black, Black British, Caribbean or African** African Caribbean Any other Black, Black British, or Caribbean background (5)
- Mixed or multiple ethnic groups** White and Black Caribbean White and Asian White and Black African Any other Mixed or multiple ethnic background (6)
- White** English, Welsh, Scottish, Northern Irish or British Irish Gypsy or Irish Traveller Roma Any other White background (7)

Other ethnic group Arab Any other ethnic group (8)

What is your height?

In centimetres: (1) _____

OR in feet and inches: (2) _____

Prefer not to say (4)

What is your weight?

In kilograms: (1) _____

OR in stone and pounds: (2) _____

Prefer not to say (4)

How often, on average, over the past year have you eaten out (e.g., at a restaurant, café)?

Not in the last year (1)

Less than once per month (2)

1 - 3 times per month (3)

1 - 2 times per week (4)

3 times per week or more (5)

End of Block: Demographics

Start of Block: Health motives

Several different factors influence our choice of food. Read each item carefully and decide how important the item is to you. There are no right or wrong answers, we are interested in what is important to you. It is important to me that the food I eat on a typical day...

	Not at all important (1)	A little important (2)	Moderately important (3)	Very important (4)
Contains a lot of vitamins and minerals (1)				
Keeps me healthy (2)				
Is nutritious (3)				

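### The primary PME model adjusts for health motives measured only after the menu has been seen, and the aim-awareness analysis names a main effect where testing moderation needs an interaction

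*Combined protocol and SAP*

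**What the plan says.** **Health motives.** The primary analysis is a linear regression of PME on label condition, with education, health motives, age and gender as covariates. On health motives the Primary section says: "Health motives (continuous) will be included as a covariate as this may predict outcomes". The same covariates go into the awareness, secondary and exploratory regressions.

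The scale is given after exposure. The Procedure section says: "After finishing their meal, participants will be asked to fill out an online questionnaire", and health motives are among its topics. The Study flow table puts them at the end: "Finally, participants will answer questions on demographic characteristics (including frequency of eating OOH) and health motives". Appendix E confirms that they form the last block. The screening questionnaire (Appendix A) has no such item.

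Two features bear on how far the score could move. The items are worded generally: "It is important to me that the food I eat on a typical day". Also, before reaching them, "both groups will be shown an image of the labelled menu"; controls are told: "Here is a slightly different version of the menu you ordered from".

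**Aim awareness.** The Sensitivity section plans two analyses. One repeats the models without participants who guess the aims; it has no trigger. The other applies if many participants guess (more than 25% is the example) and asks whether awareness moderates the label effect, by adding awareness as a categorical covariate. No interaction term is named. Under Aim guessing, awareness means guessing that the study concerns the influence of food warning labels on food choice. Appendix E asks the question after the meal, before controls have seen any label.

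**The concern.** That a variable may predict the outcome is a good reason to adjust for it when it is measured before the intervention. Randomisation then makes it independent of condition, apart from chance, and adjustment gains precision. A variable recorded after the menu, the order and the meal has no such protection. The labelled menu warns about blood pressure, heart disease and stroke, and the scale asks how important it is that food is healthy, so a shift is plausible, though not shown. If there is one, the adjusted coefficient no longer estimates the total effect of the labels.

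Education, age and gender are also asked after the meal, but they are on the screening form too and the labels cannot plausibly change them. The concern is with health motives only.

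The aim-awareness problem is confined to the sensitivity analyses. A main-effect covariate yields one label coefficient and says nothing about whether the effect differs between aware and unaware participants. Awareness is also recorded after exposure and defined by something only one arm has seen, so guess rates will probably differ by arm. Removing guessers then compares groups that were not formed by randomisation, and a changed effect could be read as demand effects when it may be selection.

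**Working it through.** **Inputs from the documents (Sample size and Multiple comparisons sections).** 130 per condition, d = 0.35, two-sided alpha 0.05, 80% power; cited PME effects d = 0.58-0.63.

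**Assumed inputs (the documents give none).** Within-arm correlation r of health motives with PME: 0.3, with 0.2-0.4 for the standard error. Label-induced shift s in health motives: -0.2 to +0.2 SD. Guess rates q1 (label arm) and q0 (control arm), and the PME gap between guessers and non-guessers: as below. Clustering by table is ignored throughout; it would lower the power figures.

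**1. The plan's own figure.** A two-sample t test with d = 0.35 needs 129.1 per arm, so 130 per arm and 260 in all. Power at 130 per arm is 80.3%. The stated N reproduces.

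**2. Bias from the post-exposure covariate.** Adjusted effect = d - r × s. Residual SD = sqrt(1 - 0.3²) = 0.954.

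| True d | s (SD) | Adjusted effect | Power |
|---|---|---|---|
| 0.35 | -0.2 | 0.35 + 0.06 = 0.41 | 93% |
| 0.35 | 0 | 0.35 | 83.8% |
| 0.35 | +0.2 | 0.35 - 0.06 = 0.29 | 68% |
| 0.58 | +0.2 | 0.58 - 0.06 = 0.52 | 99.2% |

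Without the covariate, power is 80.3% at d = 0.35 and 99.7% at d = 0.58. Simulation agrees: 4,000 trials with d = 0.35 and s = +0.2 gave a mean of 0.289 adjusted and 0.349 unadjusted. If the true total effect is zero, a 0.2 SD shift raises the rejection rate from 5% to about 8%.

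**3. Would comparing arm means settle it?** Power to detect a 0.2 SD shift with 130 per arm is 36.2%. The 95% margin is 1.96 × sqrt(2/130) = 0.24 SD. Similar means would not show that there was no shift.

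**4. Cost of leaving the covariate out.** Standard error ratio = 1/sqrt(1 - r²) = 1.02, 1.05 and 1.09 for r = 0.2, 0.3 and 0.4.

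**5. Excluding guessers.** Effect after exclusion = 0.35 - (q1 - q0) × gap, with the gap from -0.3 to +0.3 SD.
- 20% v 5% guessing: 0.35 ± 0.15 × 0.3 = 0.395 to 0.305.
- 50% v 5% guessing: 0.35 ± 0.45 × 0.3 = 0.485 to 0.215.

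**6. Interaction.** With equal arms, the 25% trigger needs (q1 + q0)/2 > 0.25; for q0 = 0.05 that means q1 > 0.45. The standard error is sqrt[1/(130 q1) + 1/(130(1 - q1)) + 1/(130 q0) + 1/(130(1 - q0))], and the effect detectable with 80% power is 2.80 times that.
- 50% v 5% (27.5% overall): 0.439 × 2.80 = 1.23 SD.
- 40% v 15% (27.5% overall): 0.304 × 2.80 = 0.85 SD.
- No control aware: the design matrix has rank 3 of 4, so the interaction cannot be estimated.

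For contrast, in simulated trials where the label effect differed by 0.50 SD between aware and unaware participants, the main-effect model returned a single label coefficient of about 0.35 and no sign of the difference. The interaction model recovered it.

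**The case against.** Nothing in the documents shows that the labels move health motives. The scale has trait wording, and both arms have seen the labelled menu before answering it, so only a residual difference between arms can bias the estimate. For small shifts the planned model does about as well as the alternative: at r = 0.3, a +0.05 SD shift gives 0.335 and 80.5% power, and +0.1 SD gives 0.32 and 76.8%, against 80.3% without the covariate. The covariate also has a stated prognostic purpose, and dropping it costs precision. If clustering is found, the plan moves to mixed models for which it names no covariates, so it is unclear whether health motives would be in the final PME model at all. On moderation, the intention is plain and the wording may be loose shorthand for an interaction. The Sensitivity section also accepts guesses that are similar to the stated aim, which leaves some room for controls to be coded aware.

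Most of this stands as a limit on size, and it keeps the point modest. It does not make the covariate pre-exposure. Nor does showing controls the image equalise the arms: one arm chose and ate a meal with the labels in view, the other saw a picture afterwards. The moderation sentence, followed as written, still does not answer its own question.

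**Conclusion.** Both parts hold. The first is conditional: the adjustment is unbiased only if the labels leave the health-motives score unchanged, which the trial can check only weakly. Under the assumed r = 0.3 and shifts of up to 0.2 SD either way, the error is at most 0.06 SD on d = 0.35. That can matter for significance near the planning effect and would rarely matter at the cited 0.58. The primary estimate need not carry this assumption when a model without the covariate costs so little. N = 260 is unaffected.

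The second part is certain but narrow. The moderation rule cannot deliver what it promises, and the exclusion of guessers is a non-randomised comparison. The main analyses keep all participants and are untouched by it. The point should be corrected; it does not put the trial's validity in doubt.

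**What to change.** **Health motives.** Make the models adjusted for age, gender and education the main analyses, and report the models that add health motives as sensitivity analyses. State the covariates for the mixed models in the same way. Report health motives by arm as description only. The cost is SAP wording and a standard error about 2-9% larger for r = 0.2-0.4.

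Alternatively, keep the covariate and ask the six items before the menu is shown. One place is after the consent step already planned ("All participants will be asked to verbally consent to taking part in the study"). Another is the screening stage, since "Guests will be pre-screened in advance to ensure eligibility", although guests consent only at the restaurant, so that would need to be covered in what they are told. Either changes the questionnaire order. Asking just before ordering carries the greater risk of priming food choice.

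**Aim awareness.** Replace the covariate wording with a condition by awareness interaction under the existing 25% trigger, labelled exploratory, and state that it is not estimable if no or almost no controls are aware. Report guess rates by arm, and describe the analysis without guessers as a non-randomised comparison. This needs no new data and no change to N; the interaction will be imprecise.

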Information sheet and informed consent	
 - Eligible participants will be e-mailed an information sheet (Appendix B) and consent form (Appendix C). Participants can ask any questions about the study via e-mail. - The researcher will schedule a study visit day, leaving 30-minute gaps between participant groups. Participants may bring a maximum of nine guests aged 18 years or older to the restaurant. - As the guests did not yet receive an online information sheet and consent form, all participants will also be provided with information by the researcher and provide verbal consent. The researcher will answer any questions prior to the study. 				
Meal choice task	
 - Participants will be invited to visit the restaurant. They will be assigned in advance to either the control or experimental condition. Any guests will be in the same condition as the primary participant (i.e., participants will be randomised by table). They will also be given a participant number which they will be required to enter in any questionnaire they complete. 				
	
  
 Control condition	Experimental condition	
   
  
 - Participants will receive a standard menu without nutrient warning labels. 	 
 - Participants will receive a menu featuring a nutrient warning label next to items high in salt. Text at the bottom of the menu will read “[label image] indicates that the salt content of this item is higher than 50% of the daily recommended limit (6g per day). High salt 	
  
	Control condition	Experimental condition	
 - Participants will receive a standard menu without nutrient warning labels. 	
 - Participants will receive a menu featuring a nutrient warning label next to items high in salt. Text at the bottom of the menu will read “[label image] indicates that the salt content of this item is higher than 50% of the daily recommended limit (6g per day). High salt
Control condition	Experimental condition				

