Appendix E – Post-exposure assessments

Please enter your participant ID. If you are unsure what this is, please ask the researcher.

Please select the letter which is circled on your sticker label. If you are unsure, please ask the researcher.

A (1)

B (2)

End of Block: Default Question Block

Start of Block: Aim guessing

What do you think was the aim of this study?

End of Block: Aim guessing

Start of Block: Food sharing

Did you share any of the food or drink items?

Yes (1)

No (2)

Display This Question:

If Did you share any of the food or drink items? = Yes

What items were shared? Please also give an estimation in % of how much of each item was shared.

Did you add any condiments (e.g., sauce, salt) to your food?

- Yes (1)
- No (2)

Display This Question:

If Did you add any condiments (e.g., sauce, salt) to your food? = Yes

What condiments did you add? Please also give an estimation in teaspoons of how much of each condiment was added.

End of Block: Food sharing

Start of Block: PME

Please consider the following statements in relation to the menu you ordered from.

Not at all (1) A little bit (2) Somewhat (3) Quite a bit (4) A great deal (5)

The menu made me concerned about the health effects of consuming items high in salt. (1)

The menu
made
consuming
items high in
salt seem
unpleasant. (2)

The menu
discouraged
me from
wanting to
consume
items high in
salt. (3)

 End of Block: PME**Start of Block: Attention check**

This question is an attention check, so please answer truthfully. How many times have you visited the planet Mars?

- Several times (1)
- Just once (2)
- Never (3)

End of Block: Attention check**Start of Block: Awareness**

Did you notice any warning labels next to any of the menu items when making your meal selection?

- Yes (1)
- No (2)

Display This Question:

If Did you notice any warning labels next to any of the menu items when making your meal selection?

= Yes

What did the label tell you about?

Healthy items (1)

Organic (2)

Calcium (3)

Sustainable (4)

Added sugars (5)

Vegetarian (6)

Unhealthy items (7)

Salt (8)

Fibre (9)

Gluten free (10)

None of these (11)

Not sure (12)

Display This Question:

If Did you notice any warning labels next to any of the menu items when making your meal selection?

= Yes

Please describe what the warning label said.

Page Break

Did you think about the salt content of the meals when making your selection?

Yes (1)

No (2)

End of Block: Awareness

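### The label-awareness odds ratio is referenced to a control arm that has no labels to notice, so it is either not finite or set by a handful of false control reports

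*Combined protocol and SAP*

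**What the plan says.** Label awareness is a primary objective and is listed under Primary outcomes in Measures. For its analysis, Statistical analysis (Measured variables, Primary) says: "Logistic regressions will be performed to assess the odds of (i) being aware of the label", "using the control menu group as the reference category", adjusted for education, health motives, age and gender. The same paragraph plans a descriptive report of awareness overall and by condition. It names no test and no method for empty or sparse cells.

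The comparison arm is described in Experimental design: "In the control condition, there will be no labels". Study flow (Meal choice task) agrees: "Participants will receive a standard menu without nutrient warning labels".

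Both arms get one identical item in Appendix E: "Did you notice any warning labels next to any of the menu items when making your meal selection". Those who answer yes are asked to describe the label, and Measures (Label awareness) adds: "Responses that mention high in salt or similar will be coded as aware". Only in the following block of Appendix E are control diners shown the labelled menu, introduced by "Here is a slightly different version of the menu you ordered from".

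**The concern.** True label awareness in the control arm is zero by design; it is not a quantity to be estimated. A control diner can be coded aware only by misreporting. That is possible: the item is self-reported and comes after three PME statements that each mention items high in salt.

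The reference odds are therefore either zero or made up entirely of errors. If they are zero, the logistic model has no finite estimate for the condition effect, and the usual Wald output would be uninformative despite an obvious difference. If they are not, the size of the odds ratio depends mainly on how many controls misreported and says little about how many labelled diners noticed the label. The stated objective is to measure awareness, and this statistic does not do so.

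A smaller ambiguity adds to this. The analysis section does not say whether the modelled outcome is the yes/no item or the free-text coding, and that choice changes the number of controls counted as aware.

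**Working it through.** **Inputs.** From Sample size: 130 per arm, and a maximum of about 500 in total, so about 250 per arm. The documents give no figure for labelled-arm awareness or for false reporting by controls. Both are assumed below and varied.

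**The plan's own figure.** For d = 0.35, 80% power and two-sided alpha 0.05, n per arm = 2(1.960 + 0.842)²/0.35² = 128.2, so 129. The t-test version gives 129.1, so 130 per arm and 260 in total. The plan's figure is reproduced; it concerns PME, not awareness.

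**Step 1: chance that no control is coded aware.** This is (1 − r)^n for false-report rate r, treating diners as independent.

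| r | n = 130 | n = 250 |
|---|---|---|
| 0.5% | 0.52 | 0.29 |
| 1% | 0.27 | 0.08 |
| 2% | 0.07 | 0.006 |
| 5% | 0.001 | <0.001 |

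**Step 2: what happens with an empty control cell.** Take 65/130 against 0/130. The adjusted logistic model, fitted with simulated covariates, did not converge. Between 10 and 100 iterations the log odds ratio rose from 11.3 to 25.1, its standard error from 24 to over 23,000, and the Wald p-value from 0.63 to 0.999. A likelihood-ratio test on the unadjusted table would reject decisively: 2 × [130 ln 0.5 − (65 ln 0.25 + 195 ln 0.75)] = 112.2 on 1 df. The estimate and the Wald test fail, but not every test does.

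**Step 3: what happens with a few false reports.** With c of 130 controls coded aware and 65/130 labelled diners aware, OR = (65/65)/(c/(130 − c)). The Wald interval uses SE = √(1/65 + 1/65 + 1/c + 1/(130 − c)). The risk difference is (65 − c)/130, with a Newcombe interval.

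| c | OR (95% CI) | Risk difference (95% CI) |
|---|---|---|
| 0 | none | 0.50 (0.41 to 0.58) |
| 1 | 129 (18 to 951) | 0.49 (0.40 to 0.58) |
| 2 | 64 (15 to 270) | 0.48 (0.39 to 0.57) |
| 5 | 25 (10 to 65) | 0.46 (0.36 to 0.55) |

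One extra false report, from 1 to 2, halves the odds ratio and moves the risk difference by less than 0.01.

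**Step 4: the same odds ratio from very different awareness.**
- 40/130 (31%) against 1/130: OR = (40/90)/(1/129) = 57; risk difference 39/130 = 0.30.
- 90/130 (69%) against 5/130: OR = (90/40)/(5/125) = 56; risk difference 85/130 = 0.65.

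**The case against.** The strongest reply is that the useful result is already planned: awareness will be described by condition, so a reader will have both proportions. This stands, and it limits the harm. But no interval is planned for the labelled-arm proportion, and the only inferential statistic on this outcome is the odds ratio.

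Second, the contrast could serve as a manipulation check. The PME statements may prompt false reports in the labelled arm as well, and the control rate is the only estimate of that background. This is fair, although the documents do not call it a check. It argues for reporting the control proportion and, if a contrast is wanted, a risk difference, which subtracts the background directly.

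Third, higher false-report rates would make the odds ratio estimable. At 10 of 130 controls and 65/130 labelled diners aware, it is 12 (95% CI 5.8 to 24.9). The estimation failure would then disappear, but the reference odds would still be nothing but misreports. The free-text coding, if used, makes low rates more plausible.

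Fourth, the pair in step 4 was chosen to match, and its intervals are wide (7.7 to 425 and 21 to 148). With controls fixed at 10, the odds ratios would be 5.3 and 27 and would separate. This is correct; the pair shows what can happen and is not a forecast.

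Finally, the natural reading is that the free-text coding in Measures defines the modelled outcome. That is likely, and a cross-reference would settle it.

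**Conclusion.** The concern holds. The planned odds ratio is not finite if no control is coded aware; otherwise its size is driven by false control reports. An empty control cell is a real prospect at low false-report rates (7% to 52% at 130 per arm for rates of 2% down to 0.5%) and very unlikely at 5%.

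The calculations rest on assumed awareness and false-report rates, are unadjusted apart from the test fit, and ignore clustering by table in steps 1 to 4. The logical point, that control awareness is zero by design, needs none of these assumptions.

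The consequence is confined to one outcome listed under Primary. It should be corrected before analysis. The PME comparison, the sample size of 260 and the interim rule do not depend on it. The parallel logistic regression for salt awareness is sound, because diners in either arm can truthfully say they thought about salt.

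**What to change.** Replace the label-awareness regression with wording such as:

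> Label awareness, coded from the free-text answer, will be estimated as the proportion aware in the labelled arm, with a 95% confidence interval allowing for clustering by table. The control proportion will be reported as the false-report rate.

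If a between-arm contrast is kept, pre-specify a risk difference with a table-clustered interval. Firth-penalised logistic regression is a fallback only. It always gives a finite estimate, but it still moves with the control count: at 65/130 labelled diners aware, adding 0.5 to each cell (equivalent to Firth for the unadjusted table) gives 261, 86, 51 and 23 for 0, 1, 2 and 5 controls. Keep logistic regression for salt awareness.

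The cost is a change of wording and one odds ratio fewer in the report; no new data are needed. At an assumed 65/130, the replacement interval is 0.5 ± 1.96√(0.25 × D/130), with design effect D = 1 + (m − 1) × ICC and an assumed m = 4 diners per table:
- no clustering (D = 1.0): 41% to 59%
- ICC 0.1 (D = 1.3): 40% to 60%
- ICC 0.2 (D = 1.6): 39% to 61%
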